The Pocket is an FDA approved device. The Pocket's outer shell is made out of medical grade ABS plastic. Medical grade and biocompatible adhesives (Loctite 4011) are used to seal the device and prevent infiltration of water and bodily fluids. The edges of the probe face are also chamfered to avoid a sharp edge so there should be minimal risk of abrasion caused by the probe with the pressure exerted.

Finally, the Pocket will undergo cleaning and high-level disinfection per the instructions for use prior to use in a patient. The reprocessing procedures have been validated by an independent third-party laboratory, Nelson Labs, and found to be a safe and effective way of infection control.

Benefits:

Women receiving the intervention may be referred to follow-up care sooner than those who do not receive the intervention (standard of care).

For participants who are La Liga health providers or administrative staff, there are no direct benefits for taking part in the study. However, they may feel a sense of satisfaction in helping inform a process that may improve future cancer screening and treatment programs (for the community), provide faster care to patients, improve patient follow-up care, and reduce deaths from this disease in the future.

11. Costs to the Subject:

There are no costs to the participants of this study.

12. Data Analysis & Statistical Considerations:

Sample size justification: With the proposed sample size of 200 women/group, we are powered to detect a difference of 13.5% or higher in loss to follow-up with 80% power at 5% level of significance. This difference of 13.5% corresponds to an odds ratio around 1.8, or a Cohen's η around 28%. For the in-depth interviews, sample size reflects number of interviews required to achieve saturation of themes. Namey et.al estimate that 8-16 interviews are needed to achieve 80-90% saturation, respectively.

Statistical analysis plan:

Quantitative data analysis will be conducted using STATA statistical software, SAS, JMP and/or MS Excel. Descriptive statistics will be generated to assess and quantify statistical properties of all the relevant variables (mean, median, standard deviation,

etc.). The difference in the proportion of women attending follow-up clinical visits between the two arms will be calculated to estimate the intervention effect at 5% level of significance level. Baseline covariates will be modeled using multivariable logistic regression to determine patient characteristics associated with loss-to-follow-up. Measures of predictive power (like R-square) and goodness of fit tests (like the Pearson chi-square) will be used to assess the fit of the regression model.

As part of the qualitative analysis plan, we will conduct applied thematic analysis on the observation notes and interview transcripts. Electronic files will be uploaded into QSR NVivo--software that supports coding and finer level re-coding of text data that enables researchers to explore how concepts fit by developing and modifying a hierarchical coding index. Thematic analysis will be conducted via an iterative process of data collection and analysis that utilizes four interrelated steps: reading; coding; data display; and data reduction. The team will use a codebook of a priori, structural codes based on the interview guide, and then a second round of coding, i.e. content coding, will be conducted to identify additional themes, ideas, or concepts. Twenty percent of transcripts will be coded by 2 team members, inter-rater reliability assessed, and discussions held to resolve coding discrepancies. We will create a summary of each interview and look across interviews for commonly named problems and solutions for each step of image acquisition, transfer, and interpretation.

Data will be summarized in the following areas: Core functionality (including expectations, and communication formats), data analytics, storage and availability, (3) Security, hosting and privacy, 4) Mobile delivery platform, 5) Monitoring and maintenance, 6) Hardware, equipment, power and connectivity needs.

In interviews with women in aim 1 and 2, we will assess satisfaction with the (a) overall experience, (b) timeliness of evaluation of cervical images and management, and (c) any barriers to attending future clinical visits.

Evaluation outcomes are summarized in table below.

Primary outcome - Efficacy

- Percentage of referred women who are lost to follow-up in intervention versus control arm

Secondary outcomes - Process

- Percentage of women approached who consented to participate in study
- Percentage of women approached who refused to participate in study
- Percentage of VIA screened women who are VIA+ (by study arm)
- Average # of days from screening to when a follow-up appointment is scheduled (by study arm)
- Percentage of women who were screened using mIVAA
- Percentage of mIVAA screened women with suspected cancer or pre-cancer by midwife
- Percentage of mIVAA screened women with suspected cancer or pre-cancer by expert
- Average # of days from screening to when expert enters feedback using mIVAA

- Percentage of mIVAA screened women with expert feedback within 0-7 days of mIVAA screening date
- Concordance between midwife and colposcopist on women with suspected cancer or pre-cancer as measured by:
 - Number of women screened positive by midwife
 - Number of women screened positive by expert colposcopist

System outcomes

- Average # of attempts per woman before a readable image is obtained by midwife
- Percentage of mIVAA screened women with at least 1 image rated as readable by expert
- Number of instances of mIVAA failure
- Number of instances of network failure

13. Data & Safety Monitoring:

The risks from participation in the study are considered minimal and commensurate with getting screened with routine methods of cervical cancer screening in Peru such as Pap smears. While no formal data and safety monitoring board is established for this study, study personnel will be instructed to report any unexpected and study-related adverse event to the local study PI in Peru, and Duke PI immediately.

14. Privacy, Data Storage & Confidentiality

Privacy during data collection:

Surveys and interviews will be conducted in mutually agreed upon locations where participants' privacy can be ensured.

Identifying information collected

The study will collect identifying information such as names, dates of birth, and mobile phone numbers to enable the prospective tracking of participants and pulling of medical records. In addition, for women enrolled at the mobile units, data from medical record will be abstracted to measure study outcomes. Mobile phone numbers provided by the participants will be used for any study-related communication.

The study will collect identification information only from health professionals and La Liga personnel, such as participants' names, dates of birth, and mobile phone numbers for reaching out to participants to complete study activities.

Data storage and confidentiality:

Specific actions to maintain confidentiality will include:

- All enrolled participants will be assigned study identification (ID) numbers to help protect their identity. Only study IDs will be recorded and stored alongside participants' survey responses, observation notes, audio files, interview transcriptions and medical record abstraction data.

- We will not collect DNI (Peruvian National Identification Document) or US social security numbers (SSN), except if required for payment of compensation.
- Enrollment logs, paper consent forms, a contact information logs will be the only linkages between study IDs and participants' identifiable data. Enrollment and contact logs will be stored separately from other record forms containing collected research data.
- Any data collected on paper will be stored in locked cabinets in secure offices.
- Interviews will be audio recorded on encrypted devices. When using Zoom's audio recording function, files will only be recorded to the local computer or device, not to the cloud. Audio recording files will be stored on encrypted device, Duke's box.com and/or Duke's secure servers. Identifiable information will be removed from audio-recording notes and transcriptions.
- Since this study is conducted in partnership between La Liga and Duke University, all study data collected by La Liga will be shared with Duke University. Data and files that may be shared with authorized study personnel at Duke include but are not limited to copies of study logs (including the enrollment log) to keep track of participant recruitment and study progress; eligibility screening data; scans of consent forms, interview/observation notes and other study paper documents; transcriptions of audio recordings; and data files and audio recordings.
- Electronic records containing identifiable participant data will be stored on secure applications and/or servers administered by La Liga (in Peru) and Duke University's Office of Technology Services (in the United States). Electronic records containing participant data, identified by a study ID, will also be stored on secure applications and/or servers administered by Medical Innovation & Technology (Peru). Electronic data transferred between Peru and the United States will be sent via Duke centrally administered Box account created by Toolkits; Box is HIPAA-compliant and encrypts files at rest and in transit. Permissions for the Box folder are provided centrally by Duke Office of Information Technology and approved by the study PIs. Data stored in mIVAA by MI&T will be transferred to La Liga and Duke via secure website. Data may be collected and shared via Qualtrics, REDCap or other secure and approved survey platforms/data capture system. All data will only be accessed by authorized study staff.
- La Liga health providers and administrative staff will capture and store digital images in mIVAA. Study IDs, personal health and clinical information will also be documented in mIVAA. mIVAA will be used through an App on password protected mobile devices such as a tablet(s) and/or in a browser through a web page on a mobile phone(s). Information collected and shared in mIVAA will be securely stored on servers managed by Peru-based Medical Innovation & Technology, developers of mIVAA. mIVAA data will be store in cloud storage, encrypted for MI&T's use only and transferred to La Liga and Duke via secure website. Data will be shared between La Liga health providers and administrative staff as well as research staff at La Liga and Duke. In the future, if mIVAA is linked to La Liga's electronic medical record platform (WebLiga), clinical data collected through mIVAA may be transferred to WebLiga.
- Long-term storage of data will be on a secure drive at Duke.
- To meet federal and state requirements, the research records may need to be reviewed by the Duke University Health System or a Peruvian IRB. If this information is disclosed to the external reviewers for audit purposes, it may be disclosed by them and cannot be covered by federal privacy regulations.

- Study documents and data containing identifiable information will be kept for at least six years after the study is completed. Audio files will be deleted once all analyses have been completed and published. All other data will be retained indefinitely.
- A description of this research study will be available on <https://clinicaltrials.gov/> as required by U.S. Law. This website will not include information that can identify you. At most, the website will include a summary of the results. You can search this website at any time.
- In the informed consent, participants will be told that they will have access to results of the study that will be published in an open access journal so that all participants have access at no cost. By agreeing to be in the study, participants consent to the publication and presentation of study results.
- All the data in the study will be treated in accordance with the Peruvian Law of Data Protection N° 29733, and all other laws and regulations that are applicable. La Liga, the coordinating center for the study, will be responsible for ensuring the protection of identifiable information.
- In publications or other materials created for study dissemination, only aggregate statistics will be reported and participants will not be named.

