Cervical cancer screening standard of care:

La Liga mobile units are set up close to busy locations (e.g., a market) in pre-selected communities. Screening is offered 9 am-3:00 pm every weekday for 1-2 weeks per community. Women receive Pap, VIA, breast, thyroid and rectal exams and each clinical encounter typically lasts 15 min (see Table 1). La Liga also has two central administrative offices and clinics (detection centers) where cancer-related screening and treatment is offered by health providers including expert colposcopists, and where administrative staff are based. Training has been conducted on use and reprocessing of the Pocket device, however it is not currently in use in clinics.

Currently, if VIA+ (any evidence of whitening after application of acetic acid; determined at the same time as the exam), women are advised during screening that follow-up clinical evaluation with a medical expert (colposcopist) is required, however no referrals for care are made until Pap smear results are received in about 30 days, unless there is a suspicion of cancer. Patient information and the diagnosis is entered into an electronic database at La Liga (WebLiga). La Liga staff contact women who screen positive and are diagnosed with cervical cancer or pre-cancer to schedule follow-up appointments for care, management and treatment. If the woman misses the colposcopy appointment, La Liga staff call to reschedule. After three attempts at rescheduling, the woman is considered lost-to-follow-up.

Table 1: Standard of care and proposed intervention (mIVAA)

Standard of care	mIVAA
Screen with VIA (IVAA) and Pap in MUs	Screen with VIA, Pap and mIVAA (digital imaging device component) in MUs
No expert review	Expert reviews digital images of the cervix remotely using mIVAA's telemedicine component and refers for follow-up appointments for care, management and treatment, if positive
Refer women for colposcopy based on Pap results 3-4 weeks later	For any women not referred already, refer if needed based on Pap results, per standard of care

Perform diagnostic colposcopy and biopsy and treat, if possible, at central La Liga clinic in Lima	Perform confirmatory colposcopy and biopsy and treat, if possible, at central La Liga clinic in Lima
Additional visits to complete treatment, per standard of care.	Additional visits to complete treatment, per standard of care.

Description of intervention and framework for development:

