This study's intervention will be referred to as mIVAA. mIVAA is comprised of two components: 1) a digital image capture device for magnification and documentation of the cervix during VIA screening done by midwives staffing La Liga's mobile units. Digital imaging devices used in this study will be the Pocket (device developed at Duke University) and/or digital camera of a mobile phone; and 2) a telemedicine platform that enables two-way communication between midwives and colposcopists (Gynecologist-Oncologist). mIVAA can facilitate visual inspection of the cervix through magnification and documentation for midwives, and allows for remote evaluation of cervical images by a colposcopist to determine the need for follow-up clinical evaluation for women with a positive VIA screen.

mIVAA will be implemented in the mobile units (MUs), with support from 1 to 4 expert colposcopists who work at La Liga detection centers in Lima. In the mobile units, midwives will acquire cervical images using a digital imaging device. The images will be transmitted to an expert colposcopists using a mobile device over cellular/WiFi networks.

We will use an adaptation of an existing telemedicine platform developed by MI&T to facilitate the evaluation of cervical images by colposcopists and communication with providers at mobile units. Women being screened in the mobile units will receive an expert evaluation of their cervical images, a management plan and a follow-up appointment for colposcopy and biopsy, as necessary, will be scheduled. As part of the study, we will assess how soon the evaluation, management plan and follow-up appointment are possible after the cervical cancer screening, i.e., within a few hours, same day, within a week etc. For women without suspected lesions, a referral will be possible as per standard of care once Pap results are available and if positive.

Aim 1: To pilot test mIVAA in a community-based setting in Peru.

Methodology:

For this aim, we will enroll approximately 102 women attending any one of five La Liga mobile units for cancer screening, and approximately 18 La Liga health providers and administrative staff.

As part of the pilot, we will:

- Test the feasibility of integrating mIVAA into the existing workflow at the mobile units.
- Assess mIVAA for image quality, network stability, challenges with image transmission, and ability and time to reach experts and receive feedback from experts (two-way communication between health providers).

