Activity 1: Use mIVAA system during VIA for consenting women

- Midwives and nurse technicians will proceed with usual care with all women who register for a cancer screening exam.
- Research staff will provide the nurse technician or midwife with a green card in the medical record that indicates that a woman has consented for the study. Research staff will verify that the name of the patient on the clinical history form/medical record matches the name on the consent.

If an enrolled woman screens positive on the VIA, the midwife will:

- Capture cervical images using mIVAA system.
- Enter relevant clinical notes in mIVAA.
- Use mIVAA to send images of the cervix, VIA result and clinical notes for each patient to participating expert colposcopist for evaluation of these images to evaluate the need for a management plan,
- For women with a positive VIA or suspicion of cancer, follow-up clinical evaluation with a colposcopist in a La Liga detection center will be scheduled

based on feedback received from these same colposcopists as per La Liga's institutional protocols.

If a consented woman screens negative (without suspected lesions or suspicion of cancer) on the VIA or does not have a VIA screen:

- Midwife will document on a screening eligibility form, whether or not she completed a VIA screen for the patient and the VIA result.
- Research staff will inform the woman that she is not eligible for the study, and therefore she will not continue with further activities.
- Further referrals may be made according to standard of care based on Pap results when available, and if positive.

Activity 2: Provide feedback on the use of mIVAA through a survey, brief interviews, and/or an individual or group interview. Discussions will assess feedback and satisfaction with the mIVAA system.

Study staff will document in Spanish La Liga provider and staff feedback, and translate to English for analysis and inclusion in any publications. Interviews may be audio recorded, transcribed and translated.

Colposcopists

Activity 1: Use mIVAA system to access patient cervical screening documentation and communicate with midwives and staff at mobile unit.

For each patient, an expert colposcopist will:

- Provide feedback on whether the patient should have a follow-up clinical evaluation.
- Rate quality of cervical image.

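### The primary outcome has no index date, time window or data cut-off, so observation time can differ between the historical controls and the mIVAA women

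*Combined protocol and SAP*

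**What the plan says.** Section 12 lists one primary outcome: "Percentage of referred women who are lost to follow-up in intervention versus control arm". The statistical analysis plan in the same section expresses the comparison as attendance: "The difference in the proportion of women attending follow-up clinical visits between the two arms will be calculated". Neither sentence gives a starting date, a duration or a cut-off. The Aim 2 hypothesis and the 77% non-attendance figure in Section 4 give none either. The only window in the outcome list, 0 to 7 days, concerns expert feedback.

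Loss to follow-up is described operationally once, in Section 5 under the cervical cancer screening standard of care. If a woman misses her colposcopy appointment, staff call to rebook. Then: "After three attempts at rescheduling, the woman is considered lost-to-follow-up". Section 12 neither adopts nor replaces this rule.

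Referral timing differs by arm:

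- **Standard of care (Section 5):** "no referrals for care are made until Pap smear results are received in about 30 days, unless there is a suspicion of cancer".
- **mIVAA:** referral follows expert image review. Its timing is left to be measured: "we will assess how soon the evaluation, management plan and follow-up appointment are possible after the cervical cancer screening", with examples from a few hours to a week. Table 1 keeps a later route open: "For any women not referred already, refer if needed based on Pap results, per standard of care".

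Control data are to be abstracted from the records of 200 women screened before mIVAA was in use. No screening dates or closing date are given. Outcomes for mIVAA women come from record review at an unstated time.

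**The concern.** A percentage lost to follow-up depends on how long each woman is observed and from when. With concurrent randomised arms, a loose definition would tend to affect both arms alike. Here the comparison is historical against prospective. Old records may have had a year or more in which a late visit could be entered, while the last mIVAA women may have had only weeks. Nothing in the plan equalises this.

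Two things are at stake. First, the arm difference can mix the effect of mIVAA with unequal record time, in either direction. Second, the two statements of the outcome are not complements under the only rule given. A referred woman who is never reached, never booked or still being called has not attended, yet has not had three rebooking attempts after a missed appointment. Two analysts could report different primary results from the same records. If the cut-off stays open until the data are seen, choosing it becomes part of the result.

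**Working it through.** **The plan's own figure.** Section 12 gives 200 per group for 13.5 points, 80% power and 5% significance (two-sided assumed). The formula is n = [1.96·√(2p̄q̄) + 0.842·√(p₁q₁ + p₂q₂)]² / Δ².

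- Loss of 70% against 56.5%: (1.336 + 0.568)² / 0.018225 ≈ 199 to 200, odds ratio 1.80, arcsine effect size 0.281. This matches all three stated figures.
- Loss of 77% against 63.5%: (1.267 + 0.538)² / 0.018225 = 179, and 194 with continuity correction.

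The sample size is therefore not in dispute, and adding a window does not by itself change it.

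**Inputs for the illustration.** From the documents: 23% attend (100 − 77), control referral at about day 30, target 13.5 points. Assumed: 23% is eventual attendance, mIVAA referral is at day 0 to 3, time from referral to attendance is exponential with mean m of 45 or 90 days, controls are observed for 365 days, and mIVAA accrual is uniform over 180 days. The data cut falls L days after last enrolment.

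**A. Unequal observation, no effect on eventual attendance.**

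Control: 0.23·[1 − e^(−(365−30)/m)], which is 22.99% for m = 45 and 22.44% for m = 90.

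mIVAA with referral at day d: 0.23·{1 − (m/180)·[e^(−(L−d)/m) − e^(−(L+180−d)/m)]}. For m = 45, d = 3, L = 30: 0.23·[1 − 0.25·(0.5488 − 0.0101)] = 19.9%. For m = 90: 0.23·[1 − 0.5·(0.7408 − 0.1003)] = 15.6%.

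mIVAA minus control, in percentage points (range over d = 0 to 3):

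| Lag after last enrolment | m = 45 | m = 90 |
|---|---|---|
| 30 days | −2.9 to −3.1 | −6.6 to −6.8 |
| 90 days | −0.8 | −3.1 to −3.2 |
| 180 days | −0.1 | −0.8 |

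Replacing 0.23 by 0.365 in the mIVAA expression (a true 13.5-point gain) with the 30-day lag gives 31.6 to 31.9% for m = 45 and 24.8 to 25.2% for m = 90. The observed gain is then 8.6 to 8.9 points or 2.4 to 2.7 points.

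**B. Common window of W days from screening, same 23% eventual attendance, mIVAA referral at day 3.**

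The difference is 0.23·[e^(−(W−30)/m) − e^(−(W−3)/m)].

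- W = 60: 0.23·(0.5134 − 0.2818) = 5.3 points for m = 45, and 4.3 points for m = 90, favouring mIVAA.
- W = 180: 0.4 points for m = 45 and 1.1 points for m = 90.

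With 200 per arm and means of 30 to 90 days, the chance of a significant result favouring mIVAA is 27 to 35% at day 60 and 3 to 5% at day 180. The nominal value is 2.5%.

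**The case against.** The strongest reply is that the documents do not show unequal periods. They give no control dates, accrual length, data cut or abstraction date. mIVAA appointments are also scheduled "based on feedback received from these same colposcopists as per La Liga's institutional protocols", so the same three-call rule may well run in both arms. A count-based rule applied alike, and allowed to finish for every woman, need not create unequal observation. This stands: a reader might infer that the periods do differ, or that calling effort differs, and neither is in the text. But a shared call count still fixes no index date and no observation time, and still leaves never-booked women unclassified. Nor does the plan say that the process must have finished before abstraction.

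A second reply is that earlier referral is how mIVAA is meant to work, and that days from screening to scheduling is already reported by arm. That is fair. The 30-day gap arises only when counting from screening, and women with suspected cancer are exempt from the Pap wait. It is a reason to choose a window long enough to separate earlier attendance from more attendance.

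A third reply is that the illustration is a chosen case. This also stands. The 365-day observation, 180-day accrual, lag and mean times are assumptions, and the result depends mainly on the lag. An artefact as large as 6 to 9 points at the 30-day lag arises only if every mIVAA woman also waits 30 days for referral. Table 1 does not support that, although women referred late on Pap results would move the figure part of the way.

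Finally, it goes too far to say that a never-scheduled woman has no outcome at all. She is a non-attender in the Section 12 comparison. The gap is that the two measures are never equated.

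**Conclusion.** The point holds in this form: the primary outcome lacks an index date, window and cut-off, and the only rule for loss to follow-up is a usual-care call count that Section 12 does not adopt. Observation time can therefore differ between arms, and the status of never-scheduled women depends on which sentence is followed. The documents do not establish that the periods actually differ.

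Under the stated assumptions, a 30-day lag after last enrolment gives a spurious deficit for mIVAA of about 3 to 7 points and shrinks a true 13.5-point gain to about 9 or to 2 to 3 points. A 90-day lag reduces the deficit to about 1 to 3 points and a 180-day lag to under 1. A common 60-day window from screening favours mIVAA by about 4 to 5 points, and a 180-day window by about 0.4 to 1.1. These figures show sensitivity and are not estimates of the actual bias. Because this is the sole primary outcome of a historical comparison and the repair is cheap, it should be settled before outcome data are abstracted.

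**What to change.** In Section 12, define the primary outcome identically in both arms as no completed colposcopist evaluation at a La Liga detection center within one fixed window from one common index date. For example, use 180 days from the mobile-unit screening date, which is long enough that the referral delay matters little. In addition:

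- State that referred women who are never reached or never scheduled count as not attending, so that attendance and loss to follow-up are complements.
- Require the full window of record time for every control and every mIVAA woman before abstraction, and ignore visits after the window in both arms.
- Add a sensitivity analysis indexed at referral, since the outcome concerns referred women and that date is also defensible.
- Keep the three-attempt rule only as a description of usual practice.

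The cost is protocol and analysis-plan wording, plus a final data cut that waits until the last enrolled woman has completed the window. The sample size need not change on this account.
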